#### 9.6.4. Effect on Desensitization Response Rate

The influence of factors described in Section 9.6.3 on treatment group differences in the desensitization response rate at 600 mg, 300 mg, and 1000 mg will be explored using

logistic regression. These analyses will be performed on the ITT and Completer populations. For the analyses in the ITT population, missing data will be based on the rules defined for the primary efficacy analysis. For the Completer population, missing data will be excluded.

The logistic regression model will include terms for treatment group and the baseline factor to be explored, and an interaction term between the baseline factor with treatment group. The odds ratio for the treatment group effect will be calculated at each level for categorical variables. The odds ratio for the treatment group effect will be calculated at 3 values for continuous variables (the 25% percentile, median, and 75% percentile). Main effects for treatment group and the baseline factor will also be calculated after dropping the interaction term from the model. A 95% confidence interval and p-value will be presented for each odds ratio using the Wald statistic. The p-value for the interaction term will also be presented and based on the Wald statistic. For categorical variables, the number and percent of responders for each level of the categorical variable by treatment arm will be tabulated.

## 9.6.5. Effect on Maximum Tolerated Dose at Exit DBPCFC

Each baseline factor described in Section 9.6.3, will independently be evaluated using the discrete hazards model similar to the model described in Section 9.5.1. These analyses will be performed on the ITT population and Completer population and PP population, if applicable.

The discrete hazards model will include terms for treatment, the baseline factor to be explored, and an interaction term between the baseline factor with treatment will be included. The hazard ratio for the treatment effect will be calculated at each level for categorical variables. The hazard ratio for the treatment effect will be calculated at 3 values for continuous variables (the 25% percentile, median, and 75% percentile). Main effects for treatment and the baseline factor will also be calculated after dropping the interaction term from the model. A 95% confidence interval and p-value will be presented for each hazard ratio using the Wald statistic. The p-value for the interaction term will also be presented and based on the Wald statistic.

# 9.6.6. Imputation of MTD based on Maximum AR101 Dose Achieved

Subjects who do not undergo the Exit DBPCFC have the MTD for the Exit DBPCFC imputed as the MTD at the Screening DBPCFC, as described in Section 7.4.3. As an exploratory analysis, subjects randomized to AR101 who do not undergo the Exit DBPCFC will have their MTD for the Exit DBPCFC imputed as the higher of the Screening DBPCFC MTD or the highest Exit DBPCFC dose level (1, 3, 10, 30, 100, 300 mg) less than or equal to the highest tolerated dose of randomized study treatment tolerated during Up-dosing. The highest tolerated dose is defined as the highest dose level taken for

at least two weeks, which is not immediately followed by a dose reduction or withdrawal from the study.

The number and percent of subjects by their MTD at the Exit DBPCFC will be summarized for the AR101 treatment group with this imputation scheme, with missing Exit DBPCFC imputed using their MTD at screening, and without any imputation.

# 9.6.7. Cutoff Predictive of MTD $\leq$ 30

For both ps-IgE and SPT wheal diameter, analyses may be performed in a post-hoc manner to identify cutpoints, with good performance characteristics, that discriminate between subjects eligible for randomization (MTD $\leq$ 30 mg) versus those not eligible (MTD>30 mg). Performance characteristics to be considered, include positive predictive value (PPV), sensitivity, and specificity.

## 9.6.8. Relationship of ps-IgE and SPT on Premature Discontinuations

The influence of ps-IgE and SPT wheal diameter on failure to achieve the target dose of 300 mg/d (and similarly of subjects who develop gastrointestinal symptoms and discontinue prematurely) may be explored in a post-hoc manner using logistic regression using the methods described in section 9.6.3. Additionally, the methods described in Section 9.6.7 will be used to identify cutoffs for ps-IgE and SPT wheal diameter predictive of failure to achieve the target dose of 300 mg/d (and similarly of subjects who develop gastrointestinal symptoms and discontinue prematurely).

These analyses will be performed on the ITT population.

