# 4.2. INTENT-TO-TREAT (ITT) POPULATION

The ITT population (i.e., the Full Analysis Set) will consist of all randomized subjects who received at least one dose of randomized study treatment. Subjects will be analyzed according to randomized treatment. The ITT population will be used as the primary analysis population for all analyses of efficacy endpoints. If no subjects received the incorrect treatment, the ITT population will be the same as the safety population.

Since only four subjects were randomized but not treated and due to the double blind nature of the trial, no bias is introduced by excluding these four subjects from the ITT population.

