#### 6.2. SUBGROUP ANALYSES

The primary analysis of efficacy and safety data will be performed in pediatric subjects ages 4-17. Additional analysis will be performed using the following subgroups of age, geographic region, or both age and geographic region.

Age Group:

- Ages 4-11 Years
- Ages 12-17 Years
- Ages 18-55 Years
- Ages 4-55 Years

Geographic Region:

- North America (NA)
- Europe (EU)

For countries with at least 3 subjects in each treatment arm, subgroup analyses may be performed by country.

In select analyses, age group and/or region will be included as factor(s) in the statistical analyses. When any region has fewer than 3 subjects with an evaluable response for the variable of interest in either treatment arm, region will be excluded from the model.

In addition to subgroup analyses described above, additional population subsets may be defined and utilized for select analyses. These subsets will include the following:

Baseline ps-IgE:

- $< 100 \text{kU/L} \text{ versus} \ge 100 \text{kU/L}$
- Cutoff predictive of screening MTD ≤30 mg (as determined from the Screened Population, see Section 9.6.6.)

Baseline SPT wheal diameter:

- < 8mm versus  $\ge 8$ mm
- Cutoff predictive of screening MTD ≤30 mg (as determined from the Screened Population, see Section 9.6.6)

Additional subgroups for ps-IgE and SPT wheal diameter may be defined (e.g., those predictive of subjects who fail to reach the target dose of 300 mg, see Section 9.6.7) and evaluated in exploratory analyses. These will be described as such in the study report.

Other subgroups:

- Asthmatic subjects
- Subjects enrolled in protocol ARC004

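### The SAP looks for ps-IgE and SPT cutoffs predicting failure to reach 300 mg/d in both arms together, without validation, so PPV is likely to be too low and NPV too high for patients on AR101

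*SAP*

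**What the plan says.** SAP 9.6.8 has two parts. The first is a regression of failure to reach 300 mg/d on ps-IgE and SPT wheal diameter, which "may be explored in a post-hoc manner using logistic regression using the methods described in section 9.6.3". That route leads to the model in SAP 9.6.4: "The logistic regression model will include terms for treatment group and the baseline factor to be explored, and an interaction term" between factor and treatment. The second part is the cutoff search: the methods of SAP 9.6.7 "will be used to identify cutoffs for ps-IgE and SPT wheal diameter predictive of failure to achieve the target dose of 300 mg/d". It also covers subjects with gastrointestinal symptoms who stop early. Of both parts the section says "These analyses will be performed on the ITT population".

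SAP 9.6.7 was written for eligibility at screening, before anyone is treated. On how a cutoff is judged it says only: "Performance characteristics to be considered, include positive predictive value (PPV), sensitivity, and specificity". It names no selection rule, treatment term or validation step.

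SAP 4.2 defines the analysis set: "The ITT population (i.e., the Full Analysis Set) will consist of all randomized subjects who received at least one dose of randomized study treatment". Allocation is 3:1 (SAP 2.3), so about a quarter of the set is on placebo.

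SAP 6.2 allows further ps-IgE and SPT subgroups to be defined, giving as an example "those predictive of subjects who fail to reach the target dose of 300 mg". They may be defined "and evaluated in exploratory analyses. These will be described as such in the study report". SAP 2.3 classes subjects who do not reach 300 mg/d as non-responders for the primary analysis.

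**The concern.** Failing to reach 300 mg/d for lack of tolerability is mainly an event of active treatment. A placebo subject usually counts as a non-failure whatever the ps-IgE or wheal size. A cutoff judged in both arms together therefore describes a mixture that no patient belongs to. A family considering AR101 needs the PPV and NPV on AR101, and the error in the NPV is on the reassuring side.

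The second problem is reuse. The cutoff is chosen because it separates failures from non-failures, and failures are non-responders by definition. Applied to the same subjects, it will tend to show a difference in response even if the marker carries no information.

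**Working it through.** SAP 9.6.8 states no figure to reproduce. The Phase 2 input does reproduce: 23/29 = 79.3% reached 300 mg/d on AR101 (protocol 1.1), so 6/29 = 20.7% did not.

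**Inputs.** AR101 failure is 20.7%. Placebo failure in ARC001 is 0 of 26, since protocol 1.2.2.1 describes all 26 placebo subjects as completers; the exact 95% interval is 0-13%. There are 495 children, about 371 on AR101 and 124 on placebo (protocol 9.4). AR101 response is 50% (protocol 9.4). Placebo failure of 5-10% and its independence of the marker are my assumptions.

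**Dilution.** Randomization makes the share of subjects above any cutoff equal in the two arms, apart from chance. Hence

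PPV(both arms) = 0.75 × PPV(AR101) + 0.25 × PPV(placebo).

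Take a marker with sensitivity and specificity of 0.7 on AR101:

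- Marker-positive share: 0.7 × 0.207 + 0.3 × 0.793 = 0.383.
- PPV on AR101: 0.145/0.383 = 38%.
- Both arms, no placebo failures: 0.75 × 0.378 = 28%.
- Both arms, 7% placebo failure unrelated to the marker: 0.284 + 0.25 × 0.07 = 30%.
- NPV on AR101: 0.7 × 0.793/0.617 = 90%. Both arms: 1 − 0.75 × 0.101 = 92% with no placebo failures, and 1 − 0.75 × 0.101 − 0.25 × 0.07 = 91% with 7%.

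The ratio of the failure rate in both arms to that on AR101 shows how far this depends on placebo:

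| Placebo failure | Rate in both arms | Ratio to AR101 rate |
|---|---|---|
| 0% | 15.5% | 0.75 |
| 5% | 16.8% | 0.81 |
| 10% | 18.0% | 0.87 |
| 20.7% (equal) | 20.7% | 1.00 |

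**Optimism.** Trials of 371 + 124 subjects were simulated, with a Youden cutoff chosen on both arms and placebo failure of 0-10%. The Youden rule is an assumption.

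| Marker (log-odds of failure per SD) | True AR101 PPV | Apparent PPV, both arms | Apparent PPV, AR101 only, uncorrected |
|---|---|---|---|
| None (0) | 0.207 | 0.18-0.21 | 0.24 |
| Moderate (0.4) | 0.268 | 0.22-0.25 | 0.29 |
| Strong (0.8) | 0.33 | 0.26-0.29 | 0.35 |

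Choosing and judging the cutoff on the same data raises the apparent PPV and offsets part of the dilution. With no marker effect and 10% placebo failure the two cancel (0.208 against 0.207). The apparent NPV is 0.85-0.87 against a true 0.79 with no marker effect, and 0.90-0.92 against about 0.875 with a strong one. Restricting to AR101 without correction overshoots, so both changes are needed.

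**Reuse as subgroups.** With a useless marker, the best Youden value over 17 cutpoints and 50% AR101 response, AR101 response in the low-risk group exceeds that in the high-risk group by about 3 points on average if high values are fixed as high risk, and by about 5 if either direction may be chosen. Nominal p<0.05 occurs in about 7-8% of trials in the first case and about 10% in the second; 7-12% covers the variants tried.

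For the treatment difference at ARC001 rates, with a true value of 0.300 in both subgroups, the low-risk subgroup shows 0.320 and the high-risk subgroup 0.278. That is a false between-subgroup contrast of 0.042.

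**The case against.** **Arms may be kept apart.** The SAP never says the arms are merged, and SAP 6.5 and 14.2 present tables by treatment group. That default governs display. It does not say on which subjects the cutoff is chosen, and the plain reading of an analysis on the ITT population is both arms. SAP 9.6.6 names AR101 subjects explicitly where only they are meant. The treatment and interaction terms of 9.6.4 cover the regression and not the cutoff search.

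**The placebo premise is thin.** It rests on one small, shorter study, and failure to reach 300 mg/d includes non-compliance, which can occur on placebo. This stands: dilution shrinks as placebo failure rises and vanishes if the arms fail equally. Protocol Appendix 6 gives 22% early discontinuation for subjects once assigned to placebo in ARC001, but the sentence is broken in the available text. It follows a mention of ARC002, where former placebo subjects underwent the AR101 escalation schedule, so I do not use it as a placebo rate.

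**Nothing confirmatory depends on it.** This also stands. The work is exploratory and partly post hoc, and lies outside the testing hierarchy of SAP 9.3 and 9.5.

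**Stronger readings.** A reader might infer that all predictive values come out too low; only the PPV does, and only if placebo fails less often. A reader might infer that every subgroup effect is flattered; the high-risk effect is understated. A gap of about 6 points with p<0.05 in about 14% of trials needs roughly 62% response and a search in both directions, not the planned 50%. Nor does the SAP schedule these cutoffs as efficacy subgroups: SAP 6.2 only permits exploratory ones, labelled as such, and the factor list in SAP 9.6.3 omits them.

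**Conclusion.** The point holds as a low-severity improvement. As written, the cutoff search ignores treatment arm and has no validation. At ARC001 failure rates the PPV is pulled towards 0.75 times the AR101 value, before same-data optimism gives part of that back, and the NPV is too high. Reuse of the cutoffs in the same subjects, where it occurs, would bias each subgroup's treatment difference by about 1-2 points.

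These sizes rest on fewer failures on placebo than on AR101, on placebo failure unrelated to the marker, and on an assumed selection rule, since the SAP names none. The ARC003 failure rates by arm are not in the documents. Labelling the analysis exploratory limits the claims made from it but does not correct a PPV computed in the wrong population.

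**What to change.** In SAP 9.6.8, derive the cutoffs in AR101 subjects and report PPV, NPV, sensitivity and specificity there, with placebo shown separately for reference. Name the selection rule and apply a bootstrap or cross-validated optimism correction that repeats the cutoff search in each resample. Apply the same to the gastrointestinal discontinuation outcome.

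In SAP 6.2, state that efficacy contrasts in subgroups defined by these same-data cutoffs are descriptive only, without p-values, unless optimism-corrected. Removing them from 6.2 is not required, and the fixed cuts at 100 kU/L and 8 mm are unaffected. The same edit can correct the cross-references in 6.2: the failure cutoffs are in 9.6.8, not 9.6.7, and the screening-MTD cutoffs are in 9.6.7, not 9.6.6.

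The cost is a few lines of SAP text, a small resampling step and less favourable-looking exploratory figures. No new data are needed.

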# 9.7. IMMUNE TOLERANCE NETWORK (ITN) SAMPLES

Optional blood samples are collected for exploratory analysis by the Immune Tolerance Network. These analyses will be conducted separately and are outside the scope of this analysis plan. Sample collection dates and times will be listed by subject and time point. Selected analyses including demographics and baseline characteristics, medical history, and select efficacy endpoints may be performed in the subgroup of subjects participating in this substudy.

#### 9.8. INTERIM ANALYSIS

There is no interim analysis of efficacy planned for this study.

#### 9.9. DATA SAFETY MONITORING COMMITTEE

A DSMC will monitor the study for safety. The DSMC will meet periodically to review accruing safety data. The DSMC will not be prospectively provided with any efficacy data, and the trial will not be stopped for any reasons related to efficacy. The DSMC is an

independent group consisting of three clinicians and one biostatistician who have pertinent experience in the management of Adult and Pediatric patients with Peanut Allergies, as well as in the conduct and monitoring of randomized clinical trials. These individuals will be entirely independent of the conduct of the study. Further details, including treatment masking, will be provided in the DSMC Charter.

## 10. SAFETY

Safety will be assessed on the basis of extent of exposure, concomitant medications, physical examinations, and all the safety endpoints defined in Section 3.3.

Unless otherwise noted, safety data will be summarized descriptively and the Safety population will be used for all summaries of safety parameters. In general, safety data will be summarized separately by age group (Pediatric 4-17 and Adults 18-55) and overall (ages 4-55). Further breakdown by age group (Children 4-11 and Adolescents 12-17) will be provided where indicated. Safety listings will include all randomized subjects, sorted by age group and treatment group (AR101 then placebo).

# **10.1. STUDY TREATMENT EXPOSURE**

Study treatment exposure will be summarized by age group (4-17 years and 18-55 years), treatment (AR101 and placebo), and study period (initial escalation, up-dosing, maintenance, and overall). Due to data collection issues with the electronic diary, the main calculation of exposure will be based on in clinic dosing data and the dose level of the dispensed study medication.

Study Period	First Dose Date	Last Dose Date
Initial Escalation	Date of first in-clinic dose at Initial Escalation Day 1	Date of last in-clinic dose at Initial Escalation Day 1 or Day 2
Up-Dosing	The day following the date study product was dispensed at Initial Escalation Day 2	Date of first in-clinic dose of 300 mg at the End Up-Dosing 300 mg Visit. For subjects who do not reach the 300 mg dose: the latest of the last in-clinic dose during the Up- Dosing period or the date of last study drug administration as entered on the Early Termination CRF page.
Maintenance	The day following the date study product was dispensed at End Up-Dosing 300 mg Visit	Latest of the last in-clinic dose during the Maintenance period or the date of last study drug administration as entered on the Early Termination CRF page

First and last dose dates for each study period will be identified as follows:

The total amount of study product consumed will be calculated as the sum of in-clinic doses plus the estimated amout of doses taken at home. At-home doses will be estimated by calculating the number of days between in clinic visits multiplied by the dose amout dispensed at the previous in clinic visit. This definition assumes that the subject took all doses between visits. If possible, the data will be reviewed to determine if subjects were temporarily taken off study drug for a period of time and those days will be removed from the number of at-home doses.

The following calculations of study drug exposure will be made and summarized:

- Duration of Exposure (days): calculated as the date of last dose of study drug minus the date of the first dose of study drug plus one during the study period, except for the Initial Escalation period, the duration of exposure will only be 1 or 2 days depending on whether drug was taken on Initial Escalation Day 1 and Initial Escalation Day 2. Duration of exposure will be summarized using descriptive statistics for continuous endpoints as well as categorically by 28 day increments for the overall treatment period: ≤ 28 days, 29 56 days, ... 337 364 days, and >364 days.
- Total dose consumed (mg): calculated as the cumulative sum of all doses taken during the study period.
- Average dose per day (mg): calculated as the total dose consumed divided by the number of days during the study period.
- Number of unsuccessful dose increases: where an unsuccessful dose increase is defined as a single in clinic dose at a higher dose level followed by an immediate return to the previous dose level or a lower dose level.
- Number of dose reductions: where a dose reduction is defined as any decrease in dose level that does not qualify as an unsuccessful dose increase.
- Maximum dose achieved (mg/day): summarized using descriptive statistics for continuous endpoints as well as categorically using all possible dose levels: 0.5, 1, 1.5, 3, 6, 12, 20, 40, 80, 120, 160, 200, 240, or 300 mg/day.
- Time to 300 mg dosing and time to 80 mg dosing for the overall treatment period using Kaplan-Meier methodology. Time will be calculated as date of the first 300 mg (or 80 mg) dose minus the first dose date +1. Subjects who do not reach the specified dose will be censored at the date of their last study drug dose.

The non-missing valid diary entries will be used to estimate at-home dosing compliance. The following measures of compliance with at-home dosing will be calculated:

- Total number of planned at-home dosing days: calculated as the number of days where a valid diary entry was made, but excluding entries where a dose was missed because of doctor's orders.
- Percentage of planned dosing days where a full or partial dose was consumed.
- Percentage of planned dosing days where a full dose was consumed.

- Percentage of planned dosing days where a partial dose was consumed.
- Percentage of planned dosing days where a dose was missed.

At-home dosing data will be listed. Daily diary records, including date and time, whether a full or partial dose was consumed (or the dose was missed), reason for partial or missed dose will be listed. If any dose-related symptoms are present, the symptoms, onset time, and resolution time will also be listed.

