6.3 Study Treatment Visits

6.3.1 Initial Escalation

6.3.1.1 Initial Escalation, Day-1

The Initial Escalation Day-1 visit should occur within 10 days of the Screening DBPCFC and must occur within 6 weeks from the signing of the informed consent/assent form. If the Initial Escalation is not started in this time frame, written approval to rescreen the subject and/or to waive any of the screening procedures must be obtained from the Sponsor Medical Monitor.

A physician will be available at all times during the CRC peanut OIT dosing visits.

Subjects must be free from active wheezing or a flare of atopic disease (eg, atopic dermatitis), or suspected intercurrent illness prior to initiating study product dose escalation. Additionally, subjects must be fully recovered, ie back to their baseline state of health, from any preceding illness for at least 3 to 7 days, depending on the investigator-determined severity of the illness.

The following assessments/procedures will be performed during the Initial Escalation.

Day-1 visit in the CRC:

- Concomitant medication update
- Physical examination, including weight and height
- Diet (food allergen exposure) history update
- Pre-dose vital sign measurement (blood pressure, pulse rate, body temperature)
- PEFR (3 attempts are to be performed, and the best value taken). PEFR should be measured at the same time for each visit assessment.
- Administration of study product (AR101 or matching placebo), with dosing beginning at 0.5 mg and progressing in graduated doses (if tolerated) of 1, 1.5, 3, and 6 mg. Following the first dose, subsequent doses will be delivered at 20- to 30-minute intervals. The schedule for initial day dose escalation is also shown in Table 3-1.
- Post-dose vital sign measurements (blood pressure, pulse rate) within 15- to 30-minute postdose, and prior to next dose, and at 30 minute intervals thereafter, if the time between doses is extended, and for the duration of the postdose observation period.
- Monitoring for adverse events (AEs), including allergic symptoms (Section 6.7 and Section 7.2)
- Subjects will be reminded to continue to follow a peanut-avoidant diet for the duration of the study.

Subjects may have clear liquids or flavored gelatin (eg, Jell-O) during the day of the initial day escalation procedure while they are being given the desensitization doses.

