At a minimum, subjects must be observed for 90 min. $(1\frac{1}{2} \text{ hours})$ after completion of dose escalation, with vital sign measurements and assessment for signs and symptoms of allergic reaction performed every 30 minutes. Any signs or symptoms of allergic reaction will be recorded in the CRF on the appropriate Dosing Symptom/AE form.

If Day-1 dose escalation is completed with no symptoms detected after 1½ hours of post-dose observation, the subject may be sent home from the CRC. If the subject exhibited mild symptoms, the duration of the observation period should be extended to a minimum of 1 hour after resolution of the symptoms. For moderate symptoms, the observation period should be extended to a minimum of 2 hours after resolution of the symptoms. And for severe symptoms, the subject should be observed for a minimum of 3 hours after resolution of the symptoms, either at the CRC or an emergency facility, as appropriate.

Any subject deemed to have severe symptoms that include hypoxia, hypotension, or change in mental status, stage 3 anaphylaxis defined in **Appendix 3**, or who receives intensive therapy (to be determined by the investigator, but may include such interventions as IV epinephrine, intubation, or admission to an intensive care unit) for an allergic reaction at any time should be discussed with the Medical Monitor and discontinued from the study.

If dose-limiting symptoms occur at or before the 3 mg single dose, there will be no further dosing of study product, and the subject will be classified as an escalation failure and a nonresponder for the purpose of primary and key secondary analyses. The subject will be asked to return to the CRC 14 days following the last dose of study product to undergo an Early Discontinuation Visit (Section 6.5). The subject will continue to be monitored for safety until the Early Discontinuation Visit is completed or any ongoing AEs are resolved, whichever is longer.

If no dose-limiting symptoms occur during Day-1 dose escalation, or if dose-limiting symptoms occur only with the 6 mg single dose, the subject is to return to the CRC on Day-2 to confirm the tolerability of a single 3 mg dose of study product.

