#### Table 2.2 Initial Escalation Period, Day-1, Dosing Schedule

	Initial Escalation Period, Day 1, Dosing Schedule		
Day 1 Dose #	Study Product Dose (mg peanut protein or placebo)	Cumulative Study Product Dose (mg peanut protein or placebo)	
1	0.5	0.5	
2	1	1.5	
3	1.5	3	
4	3	6	
5	6	12	

Doses will be delivered at 20 to 30 minute intervals.

Subjects who are unable to tolerate a dose of 3 mg at the end of Day 1 will be considered escalation failures.

All subjects who tolerate a dose of at least 3 mg on Day 1 will return on Day 2 to receive a single confirmatory 3 mg dose under direct observation.

Subjects with either no symptoms or mild, non-dose-limiting symptoms after receiving 3 mg on Day 2 may start 2 weeks of daily dosing at 3 mg.

Subjects who experience moderate or severe symptoms after receiving the 3 mg dose on Day 2 will be considered escalation failures.

Future dose escalations will occur every 2 weeks with the initial dose increase administered in the clinical research center.

Up-dosing Period Dosing Schedule			
Up-dosing Dose #	Study Product Dose (mg peanut protein or placebo)	Interval (weeks)	% Increase
1	3	2	
2	6	2	100%
3	12	2	100%
4	20	2	67%
5	40	2	100%
6	80	2	100%
7	120	2	50%
8	160	2	33%
9	200	2	25%
10	240	2	20%
11	300	Enter Maintenance Period	25%

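### SAP 10.1 counts the scheduled step from 6 mg on Day 1 to 3 mg on Day 2 as an unsuccessful dose increase, even in subjects who tolerated 6 mg

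*SAP*

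**What the plan says.** SAP 10.1 summarises exposure by age group, treatment and "study period (initial escalation, up-dosing, maintenance, and overall". Among the listed measures are two counts:

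- The number of unsuccessful dose increases, each being "a single in clinic dose at a higher dose level followed by an immediate return to the previous dose level or a lower dose level".
- The number of dose reductions, each being "any decrease in dose level that does not qualify as an unsuccessful dose increase".

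The same list names the dose levels it has in mind: "all possible dose levels: 0.5, 1, 1.5, 3, 6, 12, 20, 40, 80, 120, 160, 200, 240, or 300 mg/day". The Day 1 doses are among them.

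On the schedule, Protocol 6.3.1.1 starts Day 1 at 0.5 mg, "progressing in graduated doses (if tolerated) of 1, 1.5, 3, and 6 mg". SAP Table 2.2 then says that everyone who tolerated at least 3 mg "will return on Day 2 to receive a single confirmatory 3 mg dose under direct observation". Protocol 6.3.1.1 sends two groups to that Day 2 dose: "If no dose-limiting symptoms occur during Day-1 dose escalation, or if dose-limiting symptoms occur only with the 6 mg single dose". Subjects with dose-limiting symptoms at or before 3 mg receive no further study product.

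**The concern.** The definition is meant to capture an up-dose that was tried in clinic and then abandoned. It is written purely in terms of the dose sequence, and one planned step has exactly that sequence. Day 1 ends on a single in-clinic 6 mg dose and Day 2 goes back to 3 mg by design. The rule therefore scores an event for subjects in whom nothing went wrong.

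At stake is whether a descriptive safety table can be read at face value. A reader of the Initial Escalation or Overall column would take the count as attempted increases that did not hold, when much of it may be a feature of the schedule that is present in both arms.

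**Working it through.** The documents state no figure for this measure, so there is nothing to reproduce. The check applies the two definitions literally to the planned dose sequence.

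**Does the planned step qualify?** The sequence is 0.5, 1, 1.5, 3, 6 mg in clinic (Day 1), 3 mg in clinic (Day 2), 3 mg/d at home for 2 weeks, then 6 to 240 mg in 2-week steps, then 300 mg.

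- 6 mg is higher than the preceding 3 mg, is given in clinic and is given once.
- The next dose, 3 mg, is the previous level.
- Both days fall in Initial Escalation under the dose-date table in SAP 10.1, so the event lands there and in Overall.
- If the step were ruled out of the first count, it would still be a decrease in level, and the second definition would make it a dose reduction.

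**Four records:**

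| Course | Initial Escalation count | Overall count | True Overall count |
|---|---|---|---|
| Tolerates 6 mg, no later failed up-dose | 1 | 1 | 0 |
| Tolerates 6 mg, one later failed up-dose | 1 | 2 | 1 |
| Does not tolerate 6 mg, tolerates 3 mg on Day 2, no later failed up-dose | 1 | 1 | 1 |
| Stopped at or before 3 mg on Day 1 | 0 | 0 | 0 (no return to a lower dose, though escalation failed) |

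In the first row the Up-dosing and Maintenance counts are 0, and so are dose reductions. Rows 1 and 3 show that the Initial Escalation count is the same whether or not 6 mg was tolerated. Row 4 shows that the Day 1 failures at or below 3 mg score zero. With the planned step left out of both counts, the first subject scores 0 and 0.

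**How many subjects make the step?** No passage gives this, so it is shown as a range.

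- Treated: 555 enrolled (SAP 2.4) minus 4 not treated (SAP 4.2) = 551, all ages. At 3:1 this is about 413 on AR101 and 138 on placebo.
- Assumption: all placebo subjects make the step.
- Let f be the share of AR101 subjects who make it. Total = 413f + 138.
- The lowest f shown is 23/29 = 79%, the ARC001 subjects on AR101 who went on to tolerate 300 mg at the exit challenge (Protocol 1.2.2.1). They must have passed initial escalation, so this is a cautious floor if that phase was similar in ARC001.

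| f | Subjects making the step | Share of 551 |
|---|---|---|
| 79% | 464 | 84% |
| 90% | 510 | 93% |
| 95% | 530 | 96% |
| 100% | 551 | 100% |

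These totals include subjects who did not tolerate 6 mg and are rightly counted. The false events are therefore fewer, by a number that the documents do not give.

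**Effect on the comparison of arms.** Let tA and tP be the shares of AR101 and placebo subjects who tolerate 6 mg and go on to Day 2. The mean Overall count rises by tA and tP respectively, so the difference in means (AR101 minus placebo) moves by tA − tP. If both are equal, it moves by 0. At 95% and 100% (assumption) it moves by 0.95 − 1.00 = −0.05 events per subject.

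**The case against.** The strongest reply is that this is one descriptive line in the exposure section. It is not among the safety endpoints in SAP 3.3, and tolerability is described elsewhere: in-clinic symptoms by dose level (SAP 10.6), non-responder subcategories by period (SAP 7.4.4), and Kaplan-Meier time to 80 mg and 300 mg (SAP 10.1). That stands, and it limits the weight of the point.

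It can also be argued that a single Day 1 dose is not a dose level, since Protocol 6.7.2 and 6.7.3 treat the tolerability of a dose and of a dose level separately. The wording of SAP 10.1 weakens this, because its own list of dose levels includes doses that occur only on Day 1. The duration bullet in the same list makes an explicit exception for Initial Escalation; these two counts have none.

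Three stronger readings are tempting, and the documents do not support them.

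- A reader might infer that nearly every subject is recorded as having failed escalation. Escalation failure is a separate class (SAP 7.4.4), based on not reaching a home dose of 300 mg, and this count does not feed it.
- A reader might infer that the Overall row loses the difference between arms, with almost everyone showing at least one failure. The SAP specifies the number of events, not a percentage with at least one, and table layouts sit in a separate document. The difference in mean counts is largely kept when similar shares tolerate 6 mg.
- A reader might extend the point to maximum dose achieved, since one Day 1 dose can put a subject at 6 mg/day. The categories for that measure include 0.5, 1 and 1.5 mg, which exist only on Day 1, so including Day 1 doses is deliberate.

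**Conclusion.** The point holds as a derivation error in a descriptive summary. On the SAP's literal text, each subject who tolerates 6 mg on Day 1 and takes 3 mg on Day 2 adds one false unsuccessful dose increase to the Initial Escalation and Overall counts, in both arms. This is probably most subjects, but that rests on few subjects being stopped at or before 3 mg and few not tolerating 6 mg, and the documents give neither share. The Initial Escalation count is uninformative as defined.

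Up-dosing and Maintenance counts, responder status and all efficacy analyses are untouched.

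**What to change.** Add one sentence to SAP 10.1: the scheduled Day 1 to Day 2 step counts neither as an unsuccessful dose increase nor as a dose reduction, unless the 6 mg dose was recorded as not tolerated. The exemption has to cover both counts, because removing the step from the first alone moves it into the second.

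An alternative is to start both counts at the Up-dosing Period and report Day 1 and Day 2 tolerability separately. This keeps subjects who did not tolerate 6 mg visible, and it also shows those stopped at or before 3 mg, whom the present count misses.

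Either way the cost is a short SAP edit and a change to the derivation program before database lock. No new data are needed: SAP 10.6 states that tolerability information is recorded for each in-clinic dose.
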